11.4 Measurement of Treatment/Intervention Effect

11.4.1 Target Lesions & Target Lymph Nodes

- Measurable lesions (as defined in [Section 11.2.1](#)) up to a maximum of 5 lesions, representative of all involved organs, should be identified as “Target Lesions” and recorded and measured at baseline. These lesions can be non-nodal or nodal (as defined in 11.2.1), where no more than 2 lesions are from the same organ and no more than 2 malignant nodal lesions are selected.
- Note:** If fewer than 5 target lesions and target lymph nodes are identified (as there often will be), there is no reason to perform additional studies beyond those specified in the protocol to discover new lesions.
- Target lesions and target lymph nodes should be selected on the basis of their size, be representative of all involved sites of disease, but in addition should be those that lend themselves to reproducible repeated measurements. It may be the case that, on occasion, the largest lesion (or malignant lymph node) does not lend itself to reproducible measurements in which circumstance the next largest lesion (or malignant lymph node) which can be measured reproducibly should be selected.
- **Baseline Sum of Dimensions (BSD):** A sum of the longest diameter for all target lesions plus the sum of the short axis of all the target lymph nodes will be calculated and reported as the baseline sum of dimensions (BSD). The BSD will be used as reference to further characterize any objective tumor response in the measurable dimension of the disease.
- **Post-Baseline Sum of the Dimensions (PBSD):** A sum of the longest diameter for all target lesions plus the sum of the short axis of all the target lymph nodes will be calculated and reported as the post-baseline sum of dimensions (PBSD). If the radiologist is able to provide an actual measure for the target lesion (or target lymph node), that should be recorded, even if it is below 0.5 cm. If the target lesion (or target lymph node) is believed to be present and is faintly seen but too small to measure, a default value of 0.5 cm should be assigned. If it is the opinion of the radiologist that the target lesion or target lymph node has likely disappeared, the measurement should be recorded as 0 cm.

- **The minimum sum of the dimensions (MSD)** is the minimum of the BSD and the PBSD.

11.4.2 Non-Target Lesions & Non-Target Lymph Nodes

Non-measurable sites of disease ([Section 11.2.2](#)) are classified as non-target lesions or non-target lymph nodes and should also be recorded at baseline. These lesions and lymph nodes should be followed in accord with [11.4.3.3](#).

11.4.3 Response Criteria

- 11.4.3.1 All target lesions and target lymph nodes followed by CT/MRI/PET-CT/Chest X-ray/physical examination must be measured on re-evaluation at evaluation times specified in [Section 11.1](#). Specifically, a change in objective status to either a PR or CR cannot be done without re-measuring target lesions and target lymph nodes.

Note: Non-target lesions and non-target lymph nodes should be evaluated at each assessment, especially in the case of first response or confirmation of response. In selected circumstances, certain non-target organs may be evaluated less frequently. For example, bone scans may need to be repeated only when complete response is identified in target disease or when progression in bone is suspected.

11.4.3.2 Evaluation of Target Lesions

- **Complete Response (CR):** All of the following must be true:
 - Disappearance of all target lesions.
 - Each target lymph node must have reduction in short axis to < 1.0 cm.
- **Partial Response (PR):** At least a 30% decrease in PBSD (sum of the longest diameter for all target lesions plus the sum of the short axis of all the target lymph nodes at current evaluation) taking as reference the BSD (see [Section 11.4.1](#)).
- **Progression (PD):** At least one of the following must be true:
 - At least one new malignant lesion, which also includes any lymph node that was normal at baseline (< 1.0 cm short axis) and increased to \geq 1.0 cm short axis during follow-up.
 - At least a 20% increase in PBSD (sum of the longest diameter for all target lesions plus the sum of the short axis of all the target lymph nodes at current evaluation) taking as reference the MSD ([Section 11.4.1](#)). In addition, the PBSD must also demonstrate an absolute increase of at least 0.5 cm from the MSD.
 - See [Section 11.3.2](#) for details in regards to the requirements for PD via FDG-PET imaging.
- **Stable Disease (SD):** Neither sufficient shrinkage to qualify for PR, nor sufficient increase to qualify for PD taking as reference the MSD.

11.4.3.3 Evaluation of Non-Target Lesions & Non-target Lymph Nodes

- **Complete Response (CR):** All of the following must be true:
 - Disappearance of all non-target lesions.
 - Each non-target lymph node must have a reduction in short axis to < 1.0 cm.

- **Non-CR/Non-PD:** Persistence of one or more non-target lesions or non-target lymph nodes.
- **Progression (PD):** At least one of the following must be true:
 - a. At least one new malignant lesion, which also includes any lymph node that was normal at baseline (< 1.0 cm short axis) and increased to \geq 1.0 cm short axis during follow-up.
 - b. Unequivocal progression of existing non-target lesions and non-target lymph nodes. (NOTE: Unequivocal progression should not normally trump target lesion and target lymph node status. It must be representative of overall disease status change.)
 - c. See [Section 11.3.2](#) for details in regards to the requirements for PD via FDG-PET imaging.

11.4.4 Overall Objective Status

The overall objective status for an evaluation is determined by combining the patient's status on target lesions, target lymph nodes, non-target lesions, non-target lymph nodes, and new disease as defined in the following tables:

For Patients with Measurable Disease

Target Lesions & Target Lymph Nodes	Non-Target Lesions & Non-Target Lymph Nodes	New Sites of Disease	Overall Objective Status
CR	CR	No	CR
CR	Non-CR/Non-PD	No	PR
PR	CR Non-CR/Non-PD	No	PR
CR/PR	Not All Evaluated*	No	PR**
SD	CR Non-CR/Non-PD Not All Evaluated*	No	SD
Not all Evaluated	CR Non-CR/Non-PD Not All Evaluated*	No	Not Evaluated (NE)
PD	Uequivocal PD CR Non-CR/Non-PD Not All Evaluated*	Yes or No	PD
CR/PR/SD/PD/Not all Evaluated	Uequivocal PD	Yes or No	PD
CR/PR/SD/PD/Not all Evaluated	CR Non-CR/Non-PD Not All Evaluated*	Yes	PD

* See [Section 11.4.3.1](#)

11.4.5 Symptomatic Deterioration: Patients with global deterioration of health status requiring discontinuation of treatment without objective evidence of disease progression at that time, and not either related to study treatment or other medical conditions, should be reported as PD due to "symptomatic deterioration." Every effort should be made to document the objective progression even after discontinuation of treatment due to symptomatic deterioration.

11.5 Definitions of analysis variables

Formal definitions of variables used in analyses can be found in the Statistical Considerations section of the protocol.

12.0 END OF TREATMENT/INTERVENTION

12.1 Duration of Treatment

12.1.1 CR, PR, or SD: Patients who are in CR, PR or SD will continue on therapy until disease progression.

12.1.2 Disease Progression: Give a minimum of 6 weeks of therapy. Remove from protocol therapy any patient with disease progression. Document details, including tumor measurements, on data forms.

After disease progression, patients should be followed for survival per the study calendar ([Section 5.0](#)).

12.1.3 Discontinuation of study agent: If the patient discontinues [study agent(s)], patients should be followed for survival per the study calendar ([Section 5.0](#)).

12.2 Managing ineligible and canceled patients and major protocol violations

Data must be submitted per [Section 5.0](#) for patients deemed ineligible or canceled. See also the Forms Packet for full details of data submission requirements. If a patient is deemed ineligible, they may be replaced.

12.2.1 Definitions

Cancelled Patient: A study participant who is registered to the trial but never receives study treatment.

Ineligible Patient: A study participant who is registered to the trial but does not meet all of the eligibility criteria at time of registration.

Clinical Follow-up: The follow-up period where the study participant is no longer receiving treatment, but is still following the study calendar for tests, exams, and correlative endpoints (e.g., specimen collection, quality of life, disease assessments as required by the study).

Survival Only Follow-up: The follow-up period where the study participant is monitored for long-term endpoints, is no longer receiving study treatment, and is not required to follow the study calendar for tests, exams, and correlative endpoints (e.g., specimen collection, quality of life, disease assessments as required by the study). In this follow-up period, there is a schedule in which case report forms should be submitted, but the physician visits are based on the standard of care.

12.2.2 Follow-up Requirements

Patients who are deemed ineligible may continue protocol treatment provided the treating physician, study chair, and Executive Officer agree there are no safety concerns. If the patient continues protocol treatment, all scans, tests, data submission will continue as if the patient were eligible. Notification of the local IRB may be necessary per local IRB policies.

12.3 Extraordinary Medical Circumstances

If, at any time the constraints of this protocol are detrimental to the patient's health and/or the patient no longer wishes to continue protocol therapy, protocol therapy shall be discontinued. In this event:

- Document the reason(s) for discontinuation of therapy on data forms.
- Follow the patient for protocol endpoints as required by the Study Calendar.

13.0 STATISTICAL CONSIDERATIONS

13.1 Study Overview

This randomized Phase II trial will compare the progression-free survival (PFS) of sorafenib and everolimus vs. sorafenib alone in patients with radioactive iodine refractory hürthle cell thyroid cancer. Prior studies have shown that the median PFS is generally around 4.5 months for sorafenib alone in this disease population²⁹. It is hoped that the combination of everolimus and sorafenib can increase the median PFS to at least 9 months. In addition to PFS, this trial will also compare the confirmed response rate, overall survival (OS), and adverse event rates between sorafenib and everolimus vs. sorafenib alone.

13.2 Primary Endpoint

The primary endpoint for this study will compare PFS between sorafenib and everolimus vs. sorafenib alone in patients with radioactive iodine refractory hürthle cell thyroid cancer. PFS is defined as the time from randomization to the first of either disease progression or death from any cause, where disease progression will be determined based on RECIST 1.1³⁹ and will be documented at each enrolling site with no central review planned.

Final Analysis: The primary goal is to compare sorafenib and everolimus vs. sorafenib alone, where the alternative hypothesis is that sorafenib and everolimus has improved PFS compared to sorafenib alone. We will enter 15 evaluable patients to each arm of the study using a 1:1 randomization scheme (30 evaluable patients total), unless the study is stopped early at the time of the interim futility analysis (see below). With 15 evaluable patients per arm, we have 80% power to detect an improvement in the median PFS from 4.5 to 9 months (hazard ratio (HR)=0.50), assuming a 1-sided significance level of 0.20 and an accrual rate of 1 patient per month. The primary analysis will be a comparison of sorafenib and everolimus vs. sorafenib alone using a one-sided log-rank test. This analysis will take place after an approximate 36 ~~44~~ month accrual period, and after 28 total events have occurred across both arms combined (which should happen after about 12 months of follow-up in all evaluable patients). All patients who meet the eligibility criteria, sign the consent form, and are randomized will be considered evaluable for this endpoint.

Interim Futility Analysis: The interim futility analysis will happen after 14 events are observed across both arms combined. The interim futility boundary was selected using EAST software. We selected a Rho family "Beta" spending function with rho parameter "equal" 1.015. To reject the alternative hypothesis at the interim analysis (i.e. reject sorafenib and everolimus as promising), the HR will need to be > 1 for sorafenib and everolimus vs. sorafenib alone, which corresponds to a 1-sided p-value greater than 0.50. If the HR is less than or equal to 1 (1-sided $p \leq 0.50$), the study will continue to full accrual and the final analysis will be conducted as discussed above.

13.3 Secondary Endpoints

The following endpoints will be compared between the 2 arms: confirmed response rate, overall survival, and adverse events.

Confirmed Response Rate: A patient will be classified as a confirmed response per the RECIST 1.1 criteria, if they have a partial or complete response for 2 consecutive evaluations at least 4 weeks apart. The proportion of patients with a confirmed response will be calculated and compared between the 2 arms using a Chi-square or Fisher's Exact test.

Overall Survival: Overall survival (OS) is defined as the time from study entry to death from any cause. OS will be estimated using the Kaplan-Meier method, where the log-rank test will be used to compare the 2 treatment arms.

Adverse events: The maximum grade for each type of adverse event will be summarized using CTCAE version 4.0. The frequency and percentage of grade 3+ adverse events will be compared between the 2 treatment arms. Comparisons between arms will be made by using either the Chi-square or Fisher's Exact test.

Crossover patients exploratory analysis: In the crossover group that receives everolimus alone, we will assess both the response rate and progression-free survival as an exploratory analysis.

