1.1 Sorafenib

Sorafenib has been the best studied agent in this disease. Sorafenib is an oral receptor kinase inhibitor that has multiple targets include RAF, VEGFR1-3, and platelet-derived growth factor receptor- β ³⁵. Partial response rates have been reported to be between 11.5%²⁹ and 23%²⁸. At this point in time, sorafenib is the recommend treatment for RAI-refractory thyroid cancer by the National Comprehensive Cancer Network guidelines [REDACTED] and is compendium approved for this indication. A phase III study comparing sorafenib to placebo (the DECISION trial) has been completed and it has been announced that it met its primary objective with an improvement in progression-free survival of 5 months compared to placebo. In addition, it showed that sorafenib had a partial response rate of only 12.2% with a disease control rate (complete/partial response or stable disease rate for ≥ 6 months) of 54.1% compared to 33.8% for placebo. It is notable that 18.8% of patients who received sorafenib discontinued due to adverse events⁴⁰. In addition, 77% of the patients on the sorafenib arm required a dose modification due to an adverse event, although 30.1% in the placebo arm required the same.

Despite the activity seen with sorafenib in thyroid cancer and other types of cancers, it is not clear which of the molecular targets are responsible for the anticancer effects in each tumor model. Furthermore, both phase II studies with sorafenib included subjects with all thyroid cancer cell types (i.e., papillary, follicular, Hürthle, and poorly differentiated/anaplastic).

Due to this data, National Comprehensive Cancer Network (NCCN) guidelines for the treatment of thyroid cancer specifically states that sorafenib is an acceptable treatment for RAI-refractory thyroid cancer (compendium approved) and is currently the standard of care. The FDA has granted sorafenib priority review for the treatment of RAI-refractory thyroid cancer.

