2.2 Secondary objective

To compare the confirmed response rate, overall survival (OS), and adverse event rates between sorafenib and everolimus vs. sorafenib alone.

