4.5 Re-Registration at Crossover

- Upon confirmation of progression, by the treating investigator, patients who were initially assigned to sorafenib alone will be allowed to cross over to everolimus at 10 mg q.d.
- Follow the OPEN enrollment procedures as detailed in [Section 4.3](#).

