5.0 STUDY CALENDAR

Laboratory and clinical parameters during treatment are to be followed using individual institutional guidelines and the best clinical judgment of the responsible physician. It is expected that patients on this study will be cared for by physicians experienced in the treatment and supportive care of patients on this trial.

Pre-Study Testing Intervals

- To be completed \leq 16 DAYS before registration: All laboratory studies, history and physical.
- To be completed \leq 28 DAYS before registration: Any X-ray, scan of any type or ultrasound which is utilized for tumor measurement per protocol.

	Prior to Registration	Day 1 and 15 of Cycles 1 and 2*	Day 1 of each cycle starting with Cycle 3** and after Crossover	Post-Treatment Follow-up***	Survival and Disease Status Follow-up Ψ
Tests and Observations					
History and Physical Exam	X	X	X	X	
Adverse Event Assessment	X	X	E	X	
Blood Pressure	X	X	X		
Weight	X	X	X		
Performance status	X	X	X	X	
EKG (as indicated)	X				
Fatigue/Uniscale Assessment	X				
Laboratory Studies					
Triglycerides, cholesterol π	X		X	X	
CBC w/diff, plts	X	X	X	X	
Serum comprehensive Σ	X	X	X	X	
Serologic Hepatitis B Surface Ag and Hepatitis C RNA (physician discretion, not required)	X				
Serum B-HCG	A		A		
Thyroglobulin, Serum	X		B		
Thyrotropin (Thyroid Stimulating Hormone or TSH), Serum	X		C		
Staging					
CT/MRI Tumor measurements	X		D		X

- * All evaluations during the first and second cycle may be scheduled for +/- 3 days of the scheduled day.
- ** Patient may have all evaluations for day +/- 7 days to starting treatment. For the first 2 cycles, evaluation schedule is every 2 weeks (+/- 3 days). Then for 10 cycles, evaluation schedule is every 4 weeks (+/- 7 days). After 12 cycles (48 weeks), evaluation frequency is every 8 weeks (+/- 7 days).
- *** Post treatment follow-up between 2-6 weeks after study treatment termination.
- A Serum beta human chorionic gonadotropin pregnancy test (in women of childbearing potential) **only** \leq 7 days before registration and, after crossover, \leq 7 days prior to starting treatment with everolimus only.
- B Serum Thyroglobulin does not need to be drawn if clinically not indicated (e.g., the presence of serum anti-thyroglobulin antibodies) after the baseline is done. Serum Thyroglobulin suggested at cycle 3 (+/- 7 days) and then every 4 cycles (or 16 weeks +/- 8 weeks) from the last time it was drawn.

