7.0 TREATMENT PLAN/INTERVENTION

Protocol treatment is to begin \leq 14 days of registration. For questions regarding treatment, please see the study contacts page.

This phase II randomized study is comparing sorafenib alone (standard treatment at 400 mg orally twice a day) to the combination of sorafenib (400 mg orally twice a day) and everolimus (5mg orally once a day) in patients with RAI-refractory Hürthle cell thyroid cancer. This would be a 1:1 randomization.

In patients who are randomized to sorafenib alone, we would allow for a crossover to everolimus alone (10 mg orally daily) at time of progression as an exploratory cohort. If a patient does crossover to everolimus alone, everolimus must begin within 6 weeks of the last dose of sorafenib on study. If restaging imaging has not been done within 28 days before treatment with everolimus alone, it must be repeated.

At the time of crossover, pregnancy test must be repeated. Also, if it has been more than 3 months since the last lipid profile, the lipid profile must be repeated at crossover. Other lab tests and observations will be performed per study calendar in [Section 5.0](#).

Patients will remain on treatment as long as there is no progression of disease, excessive toxicity requiring the patient to come off of treatment, or the patient withdraws from treatment.

Arm 1:

Agent	Dose and Route	Frequency	Cycle Length (ReRx)
Sorafenib*	400 mg PO	Twice daily	28 days***

Arm 2:

Agent	Dose and Route	Frequency	Cycle Length (ReRx)
Sorafenib*	400 mg PO	Twice daily	28 days***
Everolimus**	5 mg PO	Once daily	28 days***

Crossover for Arm 1:

Agent	Dose and Route	Frequency	Cycle Length (ReRx)
Everolimus**	10 mg PO	Once daily	28 days***

* Sorafenib should be taken twice daily on an empty stomach one hour before or two hours after eating. This tablet should be swallowed whole and cannot be crushed or chewed.

** Everolimus should be administered once daily at approximately the same time each day with or without food. Tablets should be swallowed whole with a glass of water. The tablets must not be chewed or crushed and grapefruit juice or grapefruit should be avoided.

***After year 1, at the start of cycle 13, the cycle length will be 56 days.

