8.3 Dose Modifications for Sorafenib + Everolimus

- If multiple adverse events are seen, administer dose based on greatest reduction required for any single adverse event observed. Reductions or increases apply to treatment given in the preceding cycle and are based on adverse events observed since the prior dose.
- Sorafenib or everolimus will not be re-escalated once reduced
- If dose reductions beyond dose lowest dose level is required OR sorafenib or everolimus is held for 4 weeks, sorafenib or everolimus will be discontinued. If 1 agent is discontinued, the patient may remain on the other agent. If sorafenib is discontinued and everolimus has never been dose reduced, the patient may have everolimus dose increased to 10 mg daily. In this scenario, dose level chart for everolimus in [section 8.4.1](#) should be used.
- If more than one of these toxicities apply, use the most stringent criteria (i.e., the greatest dose reduction.).

CTEP-AERS reporting may be required for some adverse events (See [Section 9.0](#))

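### Does Section 13.3 need a rule for adverse events that occur after sorafenib-alone patients cross over to everolimus?

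*Combined protocol and SAP*

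**What the plan says.** Section 13.3 summarises the maximum grade of each adverse-event type and then states: "The frequency and percentage of grade 3+ adverse events will be compared between the 2 treatment arms". The test is Chi-square or Fisher's Exact. No observation period is given. The crossover paragraph of the same section covers response rate and PFS, and does not mention adverse events.

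The secondary objective in Section 2.2 is to compare "adverse event rates between sorafenib and everolimus vs. sorafenib alone", together with response and survival.

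Crossover runs one way. Section 4.5, headed as a re-registration, provides that on confirmed progression "patients who were initially assigned to sorafenib alone will be allowed to cross over to everolimus at 10 mg q.d". Section 7.0 describes this as a move to everolimus alone "at time of progression as an exploratory cohort" and requires that "everolimus must begin within 6 weeks of the last dose of sorafenib on study". In the Section 5.0 calendar, the column holding the per-cycle adverse-event assessment is also labelled "and after Crossover", so these events will be in the database.

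**The concern.** Arm 1 patients can receive everolimus later, and Arm 2 patients receive it from the start. If every event is counted by randomised arm with no cut-off, the sorafenib-alone column becomes sorafenib followed, in some patients, by everolimus. That is not the contrast in Section 2.2. For toxicities typical of everolimus and rare on sorafenib, it would narrow the difference that the comparison is meant to show.

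Many patients could be affected. Section 13.2 assumes a median PFS of 4.5 months on sorafenib alone, so most of Arm 1 would progress within a year and become candidates for crossover.

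With small arms, a few patients matter. Using illustrative counts, 5/15 versus 12/15 gives a two-sided Fisher p of 0.025. Moving three Arm 1 patients into the event column (8/15 versus 12/15) gives 0.245.

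**Working it through.** **No figure to reproduce.** Section 13.3 gives no adverse-event rate, significance level or power. The 80% power in Section 13.2 belongs to PFS, which crossover does not touch because crossover follows progression.

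**Which reading the text supports.**

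| Place | What it establishes |
|---|---|
| 2.2, 13.1 | The comparator is sorafenib alone; everolimus 10 mg alone is not that treatment |
| 4.5 | Entry to crossover is a new registration, which marks where the periods divide |
| 7.0 | Crossover has its own treatment table, apart from Arm 1, and is exploratory |
| 13.3, crossover paragraph | The crossover group is analysed on its own |
| 13.3, response rate | Also has no stated cut-off, yet responses on crossover everolimus go to the crossover group |

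The response-rate row is telling. The same section is equally silent there, and the sensible reading is already clear. Nothing supports a different convention for adverse events.

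**Whether the split can be made.** Re-registration marks the start of the crossover period. Section 9.1 has solicited events graded at each treatment cycle, and Section 5.0 collects adverse events by visit. One boundary needs care. Section 9.2 assigns events up to 30 days after last treatment to the main form, while everolimus may begin at any time up to 6 weeks (42 days) after sorafenib. Since 30 < 42, everolimus can start inside or outside that tail. Where it starts inside, the analyst closes the Arm 1 period at the first everolimus dose. Arm 2 raises no parallel problem: under Section 8.3, "If 1 agent is discontinued, the patient may remain on the other agent", and such a patient is still on the randomised assignment.

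**What pooling would do.** Candidates for crossover, with exponential PFS at the planned median: 1 − 0.5^(12/4.5) = 84% of Arm 1 with a PFS event by 12 months. This describes candidates and not uptake, and it includes deaths. A second rough ceiling comes from Section 1.1, where in the phase III trial "18.8% of patients who received sorafenib discontinued due to adverse events": 1 − 0.188 = 81%. An assumed crossover share of 30–80% is therefore generous at the top.

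Let b be the grade 3+ rate on sorafenib (assumed 40–60%), c the crossover share, and q an independent grade 3+ rate on crossover everolimus (assumed 30–50%). The pooled Arm 1 rate is b + (1 − b)·c·q.

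- Smallest shift: 0.60 + 0.40 × 0.30 × 0.30 = 0.636, up 3.6 points.
- Middle: 0.50 + 0.50 × 0.50 × 0.50 = 0.625, up 12.5 points.
- Largest: 0.40 + 0.60 × 0.80 × 0.50 = 0.640, up 24 points.

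With an assumed 80% in Arm 2 and 15 per arm, exact two-sided 5% Fisher power is 44.7% at 40% versus 80%, 17.0% at 55% versus 80%, and 7.6% at 64% versus 80%. Even unpooled, a 40-point difference would be missed more often than found, so the table is descriptive in practice.

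**Pneumonitis does not size it.** Section 10.1 lists pneumonitis-type events below 1% for sorafenib. For everolimus, Section 10.2 lists pneumonitis above 10% and Section 9.4.2 places it at 20% or less. The two everolimus entries use different definitions and do not form one range. None of the figures is specific to grade 3+. Section 1.2 calls the event commonly low-grade, Section 9.1 does not solicit it, and the Section 9.2 grid requires no grade 1 entries and only treatment-related grade 2. These figures say little about the grade 3+ comparison.

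**What a split leaves behind.** Take a constant monthly first-event hazard h and a rate m of leaving treatment, so that P = h/(h + m). If Arm 1 is at 50%, then h = m. If Arm 2 stays on treatment twice as long (9 versus 4.5 months), its rate is h/(h + m/2) = 1/1.5 = 67%. Unequal time on treatment alone can separate the crude rates by 17 points under either reading.

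**The case for a change.** The best case for a change is that an implied intention is not a specified analysis. The two readings can give different answers, the events will be in the database, and one sentence would settle the matter before anyone tabulates data. The reporting window in Section 9.2 runs to the last treatment date without saying which treatment, and the stopping rule in Section 13.7 is applied by arm with the same silence.

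Much of this stands. The omission is real, and the arithmetic is right if events are pooled. Pooling can only raise the Arm 1 count or leave it unchanged.

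It does not establish a fault in the plan. The harmful result needs an analyst to label events on everolimus 10 mg as sorafenib-alone toxicity, against the objective, the separate treatment table and the re-registration. Whether pooling would leave the crude grade 3+ difference too small or too large overall is also unknown, because longer time on the combination pushes the other way. The Section 9.2 window governs which form an event goes on, not how it is analysed. Section 13.7 is a temporary-suspension trigger that the study team may adjust or pre-empt, and counting extra Arm 1 events there would make suspension more likely, not less.

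**Conclusion.** No change follows. Section 13.3 leaves unsaid a detail that the rest of the protocol points to clearly: the between-arm comparison covers initial randomised treatment, and post-crossover events belong to the re-registered cohort. A competent analyst would make that split and label the tables accordingly.

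The effect on grade 3+ rates cannot be derived from the documents. The range of about 4 to 24 points applies only if events are pooled, and it rests wholly on assumed toxicity rates, an assumed crossover share and independence between the two treatment periods. The comparison is secondary, has 15 evaluable patients per arm (17 at maximum accrual), and drives no decision. The primary PFS result is unaffected.

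The conclusion assumes that the adverse-event records carry an onset date or cycle. The calendar and the per-cycle grading suggest that they do, but the case report forms are not among the documents.
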